3.2 Number of Subjects

Ten subjects who have completed all phases of the protocol are required. In order to ensure this, it may be necessary to screen a small number of additional candidates, perhaps up to 5 total, to ensure we reach our study target of ten complete studies. For example, if an enrolled subject cannot or will not return for the second day of imaging, we will recruit and enroll a replacement subject.

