7.1 Sample Size Determination

When the sample size is 10, as planned in this pilot study, a single-group repeated measures analysis of variance with a 0.05 significant level will have 80% power to detect a difference in means across the 4 levels by an effect size of 0.32. Assuming a standard deviation at each level to be 2.2 and a between level correlation to be 0.6, the average difference will be detected in this scenario is 0.78.

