7.2 Statistical Methods

Descriptive Statistics

Primary Hypothesis: There is no difference in the number of clinically significant MM lesions detected by FDG PET/MRI, C11 PET/CT, C11 PET/MRI compared to the standard technique FDG PET/CT.

The patients will go through all of the 4 techniques and the number of clinically significant MM lesions detected by each technique will be collected. Our primary outcome is the number of MM lesions detected by each technique, which can vary from 0 to 13 with 5 or 6 lesions as an average for the MM patients. It is a repeated measures ANOVA design and our primary interest if to see if there is a within subject effect – if the number of MM lesions detected by each technique differ.

If the overall test is significant, post-hoc comparisons between the scores of the three new techniques (FDG PET/MRI, C11 PET/CT, C11 PET/MRI) and the standard technique (FDG PET/CT) will be carried out with Bonferroni correction for multiple comparison.

Secondary Hypothesis 1: There is no difference in the clarity scoring of the MM lesions among the 4 techniques.

The primary interest of Objective 2 is to compare the clarity of the detected MM lesions across the 4 techniques. A score demonstrating clarity of the lesion will be assigned to each detected lesion with higher score means clearer of the lesion image. One way repeated measure analysis of variance will be employed to detect if there is any difference among the average scores of detected MM lesion in each technique. If the overall test is significant, post-hoc comparisons between the scores of the three new techniques (FDG PET/MRI, C11 PET/CT, C11 PET/MRI) and the standard technique (FDG PET/CT) will be carried out with Bonferroni correction for multiple comparison.

Explore Objectives:

Explore which are the risk factors for having more MM lesions: CMP (Comprehensive Metabolic Panel) Glucose, Calcium, Proteins, Albumin, Total Protein, Sodium, Potassium, CO2 (carbon dioxide, bicarbonate), Chloride, BUN (blood urea nitrogen), Creatinine, ALP (alkaline phosphatase), ALT (alanine amino transferase), AST (aspartate amino transferase), Bilirubin;

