SPEP (Serum Protein Electrophoresis). Immunoglobulins, Serum Free light chains; Bone marrow biopsy % and beta-2-microglobulin level (if obtained). Linear regression model with correlated data (the MM lesions detected by each technique) will be utilized to investigate the association between the potential risk factors and the number of MM lesions detected for each patient.

Handling of Missing Data

Since our sample size is 10, and they will get their imaging done in two days, we don't anticipate any missing data.

Multiplicity

We only have one primary outcome for our primary research interest. There will be no concern of multiple testing for the overall group testing. But if we see an overall effect and we will do post-hoc comparisons of the numbers of detected MM lesions between the three new techniques (FDG PET/MRI, C11 PET/CT, C11 PET/MRI) and the standard technique (FDG PET/CT). Bonferroni correction for multiple comparison will be used to address multiplicity issue.

Interim Analysis

There will not be interim analysis for our study.

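### Minor, nearly free improvement: Holm's step-down could replace Bonferroni for the three comparisons with FDG PET/CT, at the same 5% family-wise error and with no fewer rejections

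*Combined protocol and SAP*

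**What the plan says.** Section 7.2 tests the number of lesions across the four techniques with a one-way repeated-measures ANOVA. Pairwise testing is conditional on that result: "If the overall test is significant, post-hoc comparisons between the scores of the three new techniques" and FDG PET/CT follow, and these "will be carried out with Bonferroni correction for multiple comparison". The same rule is given for the lesion-clarity scores under Secondary Hypothesis 1. The Multiplicity paragraph repeats it for the primary outcome: "Bonferroni correction for multiple comparison will be used to address multiplicity issue".

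The per-comparison level is not printed. With three comparisons the ordinary reading is 0.05/3 = 0.0167 for each. No step-down version is mentioned, and simultaneous confidence intervals are not planned. The power statement in section 7.1 concerns the overall F-test only; no power is claimed for the pairwise comparisons.

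**The concern.** Single-step Bonferroni holds every comparison to 0.0167, even after another has already been rejected. Holm tests the smallest p-value at 0.0167, the next at 0.025 and the last at 0.05, stopping at the first failure. It gives the same family-wise protection and rejects everything Bonferroni rejects. For the test decisions alone, Bonferroni therefore has no compensating advantage.

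This matters because the primary objective (section 2) asks which combinations detect more lesions than FDG PET/CT. The pairwise comparisons answer that question; the F-test does not. The four techniques form a two-by-two layout of tracer and scanner, and section 1.4 gives reasons to hope for a benefit from each. More than one true difference is therefore plausible, and that is the situation in which Holm helps. The number of completers is fixed at ten, so power gained without more patients is worth having.

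**Working it through.** **Inputs.** Section 3.2: "Ten subjects who have completed all phases of the protocol are required". Section 7.1 gives a test level of 0.05, power of 80%, four levels, an effect size of 0.32 and a detectable average difference of 0.78. Its variance inputs are stated as: "Assuming a standard deviation at each level to be 2.2 and a between level correlation to be 0.6".

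**Reproducing the plan's power.** Let V be the variance of the four technique means, and read the effect size as V / [SD² × (1 − correlation)].

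- V = 0.32 × 2.2² × (1 − 0.6) = 0.32 × 4.84 × 0.4 = 0.6195, and √V = 0.787, close to the plan's 0.78.
- Noncentrality = 10 × 4 × 0.32 = 12.8. The noncentral F with 3 and 27 degrees of freedom at 0.05 gives power 80.6%, which agrees with the stated 80%.

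**Patterns of true means**, each scaled to V = 0.6195 so that F-test power stays near 80%:

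- One technique better by d: V = 3d²/16, so d = √(0.6195 × 16/3) = 1.82.
- Both acetate techniques better by d: V = d²/4, so d = 2 × 0.787 = 1.57.
- All three new techniques better by d: V = 3d²/16, so d = 1.82.
- Additive tracer and scanner effects (0, d, d, 2d): V = d²/2, so d = √(2 × 0.6195) = 1.11.

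The plan gives no pattern of means, so all four are assumptions.

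**Comparison.** 200,000 simulated trials per pattern used normal data, compound symmetry and two-sided tests, with the F-test kept as a gate. Section 7.2 does not say whether the pairwise tests use paired t (9 df) or the pooled ANOVA error (27 df), so both are shown.

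Chance of identifying every true difference, Bonferroni to Holm:

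| Pattern | Paired t | Pooled error |
|---|---|---|
| One technique better | 51% to 51% | 63% to 63% |
| Both acetate techniques equally better | 22% to 29% | 34% to 41% |
| All three equally better | 25% to 47% | 42% to 60% |
| Additive (0, 1, 1, 2, scaled) | 7% to 17% | 12% to 23% |

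Power per truly different comparison (paired t) goes from 50.8% to 51.0% with one technique better, from 38.6% to 42.1% with both acetate techniques better, and from 50.8% to 60.8% with all three better.

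**What does not change.** Holm's first step is also 0.0167, so it never adds a first rejection. The chance of at least one significant comparison (paired t) is the same under both rules: 52.1%, 55.6% and 74.5% for the first three patterns.

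**Error control.** The highest simulated family-wise error under Holm was about 4.1% with the F-test gate and 4.6% without it.

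**The case against.** The strongest reply is that nothing in the plan is wrong. Bonferroni is valid, pre-specified and applied to a clearly stated family. No stated operating characteristic depends on it: the 80% is for the F-test, and the pairwise tests are post-hoc in a pilot whose purpose (section 3.1) is to guide a larger study. All of this stands, and it makes the point minor.

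It is also fair that the largest gain needs all three techniques to be better by the same amount, which the documents do not state. With unequal additive effects the gain is smaller in absolute terms. For assumed means of 0, 0.46, 1.49 and 1.95, the chance of identifying all three goes from 2.6% to 7.4% (paired t). If only one technique differs, there is essentially no gain.

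A reader might go further and infer that the Bonferroni rule produces a false scanner difference, by crediting only one of two equally good acetate techniques. The documents do not support that. Section 7.2 compares each new technique with FDG PET/CT only and plans no test of acetate PET/CT against acetate PET/MRI. To read one significant and one non-significant result as a scanner effect would be the reader's own error. Holm would only partly reduce the occasion for it: with both acetate techniques equally better, exactly one is credited in about 33% of trials under Bonferroni and 26% under Holm (paired t).

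Finally, a pilot may get more use from interval estimates than from tests, and intervals that match Holm are less simple. That is a real but small cost.

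**Conclusion.** This holds as a minor efficiency suggestion, not as an error. Holm keeps the 5% family-wise error and never rejects fewer hypotheses. On the plan's inputs, the gain in the chance of finding every true difference runs from about 0 points (one technique differs) to about 22 points (all three equally better, paired t), with 7 points if both acetate techniques are equally better. These sizes rest on the assumed patterns of means and on normal data for a count that section 7.2 puts between 0 and 13. That Holm never rejects fewer hypotheses does not depend on those assumptions.

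A reader might infer that the plan gives up power in general, or that its 80% is overstated because of Bonferroni. Neither follows: the F-test power and the chance of a first pairwise finding are the same under both rules.

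**What to change.** In section 7.2, under the primary hypothesis, Secondary Hypothesis 1 and Multiplicity, replace 'Bonferroni correction' with 'Holm step-down correction over the three comparisons with FDG PET/CT'. Make the change before the data are analysed. If simultaneous confidence intervals are wanted, report Bonferroni-adjusted intervals alongside the Holm decisions and say that the two can occasionally differ.

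The cost is one phrase in three places. No patients, scans or further assumptions are added.

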7.3 Subject Population(s) for Analysis

All-completed population: Only subjects who completed ALL study related procedures and follow-up will be included

8 Safety and Adverse Events

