3.6 Primary Safety Endpoints

Adverse events will be monitored through the vital signs evaluated prior to and after investigational product administration.

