4.1 Inclusion Criteria

- Patients being staged for multiple myeloma as follows: new diagnosis, high risk smoldering MM, relapsed as defined by investigator
- Patients who have undergone standard of care workup
- Patients > 20 years old.
- 300 pounds or less
- Can provide informed consent
- Scheduled for a clinically indicated F-18 FDG PET scan
- English speaking

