5.2 Treatment Regimen

C11 Acetate will be injected twice for this study on the same day. Route of administration is intravenous. Dose of each injection will be 10 mCi (370 MBq). Acceptable range 5 mCi – 20 mCi.

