PET/CT: Standard clinical Mayo Clinic whole-body PET/CT acquisition protocol.

PET/MR: PET/MRI myeloma acquisition study protocol:

	t inycloma acquisition study protocol.
Whole Body	
Station 1	
Station 2	
Station 3	
Station 4	
PET Task W	/hole Body
Bed 1 3:0	00
MRAC	1
AX LA	VA-Flex 1
Bed 2 4:	00
MRAC 2	
AX LAV	A-Flex 2
Bed 3 4:	00
MRAC 3	
AX LAV	A-Flex 3
Bed 4 3:	:00
MRAC 4	
AX LAV	A-Flex 4
Bed 5	3:00
MRAC	5
AX LAV	VA-Flex 5
Bed 6 3	:00
MRAC	6
AX LAV	VA-Flex 6
Bed 7 3	3:00
MRAC	7
AX LAV	VA-Flex 7

Comfort Modification: may remove body coils when acquisition of that area is complete, only if needed to keep the subject comfortable.

Schedule of Events 6.5

Study Activity	Day 0	Day 1 °	Day 2 ^f	Day 3 g
Informed consent	X			
History (confirm myeloma spectrum diagnosis). Record result on source document.	X			
Chart information recorded on study source document (height, weight, diabetic, pregnancy and breast feeding status, bone marrow biopsy (if obtained) %, beta-2-microglobulin level (if obtained).	X			
Vital signs prior to and following imaging sessions recorded on source document (sitting blood pressure, respiratory rate, temperature, heart rate)		X	X	
Finger-stick blood glucose prior to imaging		X	X	
CBC ^b , CMP ^c , SPEP ^d , Immunoglobulins, Serum free light chains. Within 4 weeks of study. Obtained as routine clinical tests, not research. Study coordinator will take data from EMR to enter on source/CRF.	X			
Pregnancy test (serum), if applicable ^a	X			
Adverse event evaluation. Results recorded on source document.		X	X	X
PET scans		X	X	
Follow-up call re: adverse events. Result recorded on source document.				X

^a Women of child bearing potential are required to have a serum pregnancy test. Women who are surgically sterile and/or greater than or equal to 12 months post-menopausal are not considered as child bearing potential. Pregnant women will not be allowed to participate in this study ^b CBC (complete blood count); red blood cells (RBCs), white blood cells (WBCs), platelets (PLTs), hemoglobin (Hgb), RBC

indices, and WBC differential

^c CMP (Comprehensive Metabolic Panel; if available, but not required to participate); Glucose, Calcium, Proteins, Albumin, Total Protein, Sodium, Potassium, CO2 (carbon dioxide, bicarbonate), Chloride, BUN (blood urea nitrogen), Creatinine, ALP (alkaline phosphatase), ALT (alanine amino transferase), AST (aspartate amino transferase), Bilirubin d Serum Protein Electrophoresis

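### Section 7.3 makes the lesion-count analysis depend on the Day 3 adverse-event phone call, and Section 7 names no denominator for safety

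*Combined protocol and SAP*

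**What the plan says.** Section 7.3 names a single, all-completed population: "Only subjects who completed ALL study related procedures and follow-up will be included". No other analysis set appears in Section 7.

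The protocol makes clear what follow-up is. Section 3.3 describes four visits, the last of them a phone call. The Schedule of Events (Section 6.5) lists it on Day 3 as "Follow-up call re: adverse events", within 4 days of Day 2. Section 8.1 ends the adverse event reporting period with that call.

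On numbers, Section 3.2 states: "Ten subjects who have completed all phases of the protocol are required". Sections 3.2 and 4.4 tie replacement to early withdrawal, with reasons such as declining to continue, loss of eligibility or not returning for Day 2. A missed call is not mentioned.

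The primary outcome in Section 7.2 is the number of lesions detected by each technique, which needs only the Day 1 and Day 2 scans.

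On safety, Section 3.6, headed as the primary safety endpoints, says: "Adverse events will be monitored through the vital signs evaluated prior to and after investigational product administration". Section 7 covers sample size, lesion counts, clarity scores, exploratory risk factors, missing data, multiplicity, interim analysis and the one population. It contains no summary of adverse events or vital signs.

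**The concern.** An analysis set for a within-patient imaging comparison should depend on whether the images exist and can be read. Section 7.3 adds a condition that is met or missed after imaging is finished and that carries no information about lesion counts. A complete four-technique data set could be discarded because a phone call was not completed. In a study of ten, that is a tenth of the data.

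Either consequence is avoidable. If the subject is replaced, another patient is injected and scanned to recover data already in hand. If not, the analysis runs on fewer than the ten subjects assumed in Section 7.1.

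The second part is an omission. The endpoint in 3.6 is tied to administration of the investigational product, yet the only named population is defined by completion. The plan does not say who is counted in a safety table.

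**Working it through.** **1. What the exclusion turns on.** The four scans take place on Day 1 (FDG PET/CT, FDG PET/MRI) and Day 2 (C-11 acetate PET/CT, C-11 acetate PET/MRI). The call on Day 3 asks about symptoms and the subject's experience. A subject with four scans and no call has a complete primary outcome but fails the follow-up condition in 7.3.

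**2. The plan's own power figure.** Inputs from Section 7.1: N = 10, 4 levels, alpha 0.05, effect size 0.32, SD 2.2, correlation 0.6, stated power 80%, average difference 0.78.

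- Take the effect size as V / [SD²(1 − ρ)], where V is the variance of the level means.
- Noncentrality = N × 4 × effect size = 10 × 4 × 0.32 = 12.8, with 3 and 3(N − 1) = 27 degrees of freedom and sphericity assumed.
- Noncentral F power = **80.6%**, which reproduces the stated 80%.
- SD of the level means = √(0.32 × 2.2² × 0.4) = √0.6195 = 0.787, against the stated 0.78. Entering 0.78 gives effect size 0.314 and power 79.9%.
- Reading 0.32 as Cohen's f with correlation 0.6 gives 70.4%, so that is not how the figure was obtained.

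**3. If a subject without the call is excluded and not replaced.**

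| N analysed | Noncentrality | df | Power |
|---|---|---|---|
| 10 | 12.80 | 3, 27 | 80.6% |
| 9 | 11.52 | 3, 24 | 75.1% |
| 8 | 10.24 | 3, 21 | 68.4% |

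**4. If the subject is replaced.** Section 5.2: "C11 Acetate will be injected twice for this study on the same day". Section 4.1 requires that patients be "Scheduled for a clinically indicated F-18 FDG PET scan", and Section 4.3 identifies that scan as FDG PET/CT. Each replacement therefore means 2 acetate injections and 4 − 1 = 3 scans that the patient would not otherwise have had.

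**5. How often this might happen.** The documents give no missed-call rate. As an assumption, with probability p per subject, the chance that at least one of ten fully imaged subjects is excluded is 1 − (1 − p)^10.

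| Assumed p | At least one of ten excluded |
|---|---|
| 2% | 18% |
| 5% | 40% |
| 10% | 65% |

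**6. Safety denominator (illustration only).** Suppose one subject receives acetate, has an event and stops early, and ten others complete without an event.

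- Counting completers only: 0/10 = 0%, one-sided exact 95% upper bound 1 − 0.05^(1/10) = 25.9%.
- Counting everyone injected with acetate: 1/11 = 9.1%, upper bound = 0.95 quantile of Beta(2, 10) = 36.4%.

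No text says that safety would be reported the first way.

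**The case against.** The case for leaving the plan alone has four parts.

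**Missed calls will be rare and N is protected.** The coordinator places the call and has a 4-day window. Section 3.2 foresees extra recruitment: "it may be necessary to screen a small number of additional candidates, perhaps up to 5 total". This largely stands as to size. It does not remove the rule, and replacement is not assured: a missed call is not a named trigger, so replacement depends on reading the all-phases requirement in 3.2 to include the call. That reading is possible but not certain.

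**Safety is not neglected.** A reader might infer that 7.3 hides events in subjects who stop early and makes tolerability look better than it is. The documents do not support that. Section 4.4.1 requires the Day 3 contact whatever the subject's enrolment status, with the case report documentation updated. Section 8.2 requires all adverse events in the study period to be recorded, and Section 8.5 provides for regular assessment of serious events. No text applies 7.3 to safety. Section 2 states no safety objective, and 3.6 sets no threshold or comparison. This objection stands: what is missing is a named denominator and a descriptive summary.

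**Withdrawn subjects' scans are dealt with.** A reader might see a conflict between 7.3 and the retention of withdrawn subjects' data in 4.4.1. There is none. Retention is not a promise of analysis, and the FDG scans are kept for a possible later subset analysis.

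**Incomplete imaging is dealt with.** A reader might also fault the statement in 7.2 that no missing data are expected. A subject lacking a scan is excluded and, having withdrawn, replaced, so the analysed imaging data are complete by construction.

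**Conclusion.** The point holds as a minor one. The imaging part is a stated rule: the text of 7.3, with the Day 3 call as the only scheduled follow-up, excludes a fully imaged subject for a reason unrelated to imaging. Each such case costs one four-scan data set. It leads either to one possible replacement patient or to the loss of about 5.5 percentage points of power (80.6% to 75.1%). The power figures assume the inputs of Section 7.1, sphericity and no replacement. If everyone is replaced, planned N and power are unaffected. With no missed-call rate given, the expected effect is unknown and probably small.

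The safety part is weaker. Section 7 names no safety set or summary despite the heading of 3.6, but capture of events is provided for elsewhere. The contrast of 0/10 with 1/11 shows what the choice of denominator could do, not what the plan intends.

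**What to change.** 1. In Section 7.3, define the imaging analysis set as all subjects with four evaluable scans, whether or not the Day 3 call was completed. Keep the planned repeated measures ANOVA and post-hoc comparisons on this set. Make the wording of Section 3.2 agree, so that a missed call alone does not call for a replacement.
2. State that the imaging set does not govern safety. Define a safety set of all subjects who received any study injection. Summarise adverse events and vital signs before and after imaging descriptively, by tracer received.

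The cost is a few sentences in the plan and one descriptive table. Denominators may differ between the imaging and safety tables and should be labelled. The planned test, sample size and power statement do not change.

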8.1 Definitions

Unanticipated Problems Involving Risk to Subjects or Others (UPIRTSO)

Any unanticipated problem or adverse event that meets the following three criteria:

- Serious: Serious problems or events that results in significant harm, (which may be physical, psychological, financial, social, economic, or legal) or increased risk for the subject or others (including individuals who are not research subjects). These include: (1) death; (2) life threatening adverse experience; (3) hospitalization inpatient, new, or prolonged; (4) disability/incapacity persistent or significant; (5) birth defect/anomaly; (6) breach of confidentiality and (7) other problems, events, or new information (i.e. publications, DSMB reports, interim findings, product labeling change) that in the opinion of the local investigator may adversely affect the rights, safety, or welfare of the subjects or others, or substantially compromise the research data, **AND**
- Unanticipated: (i.e. unexpected) problems or events are those that are not already described as potential risks in the protocol, consent document, not listed in the Investigator's Brochure, or not part of an underlying disease. A problem or event is "unanticipated" when it was unforeseeable at the time of its occurrence. A problem or event is "unanticipated" when it occurs at an increased frequency or at an increased severity than expected, AND
- Related: A problem or event is "related" if it is possibly related to the research procedures.

Adverse Event

An untoward or undesirable experience associated with the use of a medical product (i.e. drug, device, biologic) in a patient or research subject.

Serious Adverse Event

Adverse events are classified as serious or non-serious. Serious problems/events can be well defined and include;

- death
- life threatening adverse experience
- hospitalization
- inpatient, new, or prolonged; disability/incapacity
- persistent or significant disability or incapacity
- birth defect/anomaly

and/or per protocol may be problems/events that in the opinion of the sponsor-investigator may have adversely affected the rights, safety, or welfare of the subjects or others, or substantially compromised the research data.

All adverse events that do not meet any of the criteria for serious, should be regarded as **non-serious adverse events**.

Preexisting Condition

A preexisting condition is one that is present at the start of the study. A preexisting condition should be recorded as an adverse event if the frequency, intensity, or the character of the condition worsens during the study period.

General Physical Examination Findings

At screening, any clinically significant abnormality should be recorded as a preexisting condition. At the end of the study, any new clinically significant findings/abnormalities that meet the definition of an adverse event must also be recorded and documented as an adverse event.

Adverse Event Reporting Period

The study treatment follow-up period is defined as the end of the day 3 follow-up phone call for the study (1 day following the last administration of study treatment). This phone call concludes the Adverse Event Reporting Period.

Post-study Adverse Event

All unresolved adverse events should be followed by the sponsor-investigator until the events are resolved, the subject is lost to follow-up, or the adverse event is otherwise explained. At the last scheduled visit, the sponsor-investigator should instruct each subject to report, to the sponsor-investigator, any subsequent event(s) that the subject, or the subject's personal physician, believes might reasonably be related to participation in this study.

Abnormal Laboratory Values

All laboratory values associated with this study will be a part of the patients clinical medical record, and clinically indicated. No follow up laboratory values will be obtained following imaging.

Hospitalization, Prolonged Hospitalization or Surgery

Any adverse event that results in hospitalization or prolonged hospitalization should be documented and reported as a serious adverse event unless specifically instructed otherwise in this protocol. Any condition responsible for surgery should be documented as an adverse event if the condition meets the criteria for an adverse event.

Neither the condition, hospitalization, prolonged hospitalization, nor surgery are reported as an adverse event in the following circumstances:

- Hospitalization or prolonged hospitalization for diagnostic or elective surgical procedures
 for a preexisting condition. Surgery should **not** be reported as an outcome of an adverse
 event if the purpose of the surgery was elective or diagnostic and the outcome was
 uneventful.
- Hospitalization or prolonged hospitalization for therapy of the target disease of the study, unless it is a worsening or increase in frequency of hospital admissions as judged by the clinical investigator.

